6 STATISTICAL CONSIDERATIONS

6.1 Power Calculations for Primary and Secondary Hypotheses

6.1.1 Primary Endpoint

The primary endpoint RSFD is defined as follows.

Consistent with use of free-days in other studies, RSFDs will use a “last off” approach. This is the approach that has been used in PETAL Network studies (e.g., NCT02509078), is preferred by FDA as a more durable/sustained recovery landmark, and recommended by our External Advisory Board.

“Last off” means that RSFDs will be counted when a participant gets off and stays off of respiratory support (as defined in Section 4.1.1) to day 28. Days off of respiratory support will be counted back from day 28 to the last day when respiratory support was received. If a participant is still receiving respiratory support on day 28, no RSFDs will be counted, even if they were not receiving support for some number of days before day 28. Following are 3 examples of this calculation:

1. Participant receives respiratory support from days 1-10 and then receives no further respiratory support through day 28. RSFDs=18.
2. Participant receives respiratory support from days 1-10, then again from 16-20, then again from 24-26. No respiratory support is received on days 27 or 28. RSFDs=2.
3. Participant receives respiratory support from days 1-10, then again from 26-28. RSFDs=0.

Participants who do not survive to day 28 are assigned zero respiratory-support-free days [23, 88]. The 28-day landmark is chosen, because

1. Interventional trials in acute respiratory failure typically involve a 28-day treatment or follow-up period after the patient enrolls in the trial; and
2. Most patients with acute respiratory failure have either died or been successfully weaned from respiratory support by day 28 [23, 88].

To estimate the required sample size for the trial with adequate statistical power for the primary endpoint, we used the data of VFDs in the ganciclovir and placebo arms of the GRAIL Phase 2 trial and available RSFD data in the literature [83-85]. The summary statistics of VFDs in the sepsis cohort of GRAIL Phase 2 trial are shown in the table below. Since standard deviation data for RSFD is sparse, we assume that standard deviation for RSFDs is similar to that of VFDs in our sample size calculations as informed by Table 6-1.

Table 6-1. Summary statistics of VFDs in the Sepsis Cohort of GRAIL Phase 2 Trial

	n	Min	Q1	Med	Mean	Q3	Max	StD
Control	66	0	9.0	20	16.33	24	27	9.62
Treatment	71	0	16.5	23	19.07	25	27	9.25

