Total	137	0	13.0	23	17.75	25	27	9.50

The sample size of the Phase 3 trial was determined for the primary endpoint, accounting for mortality, realistic and clinically relevant mean difference in RSFD between the arms, and feasibility.

Assume that RSFDs follow a normal distribution within group 1 (ganciclovir) and group 2 (placebo), respectively.

$$RSFD_{1,i} \sim N(\mu_1, \sigma_1^2), \quad i.i.d., \quad i = 1, \dots, n_1$$

$$RSFD_{2,j} \sim N(\mu_2, \sigma_2^2), \quad i.i.d., \quad j = 1, \dots, n_2$$

The hypotheses are then:

$$H_0: \mu_1 = \mu_2$$

$$H_1: \mu_1 = \mu_2 + d,$$

where d is the difference between the means.

Assume equal sample sizes, the sample size in each randomization group can be calculated using the following formula:

$$n = 2 \left(t_{1-\frac{\alpha}{2}, 2n-2} + t_{1-\beta, 2n-2} \right)^2 \left(\frac{\sigma_{pooled}}{d} \right)^2, \text{ where}$$

n = estimated sample size for each randomization group $t_{1-\frac{\alpha}{2}, 2n-2} = \left(1 - \frac{\alpha}{2}\right)^{\text{th}}$ quantile of t_{2n-2} distribution (with $2n - 2$ degrees of freedom)

$t_{1-\beta, 2n-2} = (1 - \beta)^{\text{th}}$ quantile of t_{2n-2} distribution (with $2n - 2$ degrees of freedom)

σ_{pooled}^2 = pooled variance of both groups

Note that n in the above equation does not have an explicit form, and thus, we use `pwr.t.test` in CRAN library `pwr` to derive sample size for the two-sample t-test here.

Although distributional information for RSFD is limited in the literature, based on data that we do have available we anticipate the variance of RSFD to be similar to that of VFD. The pooled variance σ_{pooled}^2 was estimated from the GRAIL Phase 2 trial to be 9.4^2 , which has been used as an estimate for σ_{pooled}^2 in our power calculations. A matrix is given below in Table 6-2. The numbers correspond to the estimated sample sizes required in each arm to achieve 80 - 90% power for various settings for difference in the means (minimum detectable difference in RSFDs between the two arms; 2.5 – 3 days) and the assumption that the pooled standard deviation of

RSFDs is 9.4 days, same as the estimate of σ_{pooled} for VFDs in GRAIL Phase 2, and at a type I error rate of 5%.

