Table 6-2. Single arm sample size required to detect a minimum difference of 2.5 – 3 days between the mean of RSFDs in the two arms, with different levels of power (80 – 90%), with the assumptions that pooled standard deviation of RSFDs in the two arms is 9.4 days (same as the estimate of σ_{pooled} for VFDs in GRAIL Phase 2), and at a type I error rate of 5%.

Single arm Sample Size			
Power	Detectable difference (d)		
	2.5 days	2.74 days	3 days
80%	223	186	156
85%	255	213	178
90%	299	249	208

Note: Although RSFDs (or VFDs) can be considered as the number of event days out of the total 28 days, and conceptually a binomial assumption may be preferred, it is nevertheless not feasible for the RSFDs (or VFDs) given their complex definition involving both mortality and actual respiratory support (ventilator) usage. For the GRAIL Phase 2 Trial, the standard deviation (SD) of VFDs, assuming a binomial distribution, is estimated to be 6.67 days, smaller than the empirical estimate of 9.4 days, which suggests a substantial over-dispersion. Thus, normal assumption with empirical variances (as obtained from the GRAIL Phase 2 Trial and given that we anticipate variance for RSFDs to be similar to that of VFDs) instead appears to be justified for RSFDs. Also note that considering that there is no substantial literature on the distribution of RSFDs, our trial design relies on GRAIL Phase 2 data on VFDs instead and our belief that variability in RSFDs will be similar to that of VFDs. However, to safeguard against the case if variance of RSFDs is substantially larger than that of VFDs, we have planned to conduct a sample size re-estimation analysis after ~50% of the endpoints have been observed (see Section 6.5.3).

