Alternative approaches to Analyze RSFDs. Our secondary analysis plan also includes a pipeline for exploring alternative approaches to analyze RSFDs. Given that RSFDs are increasingly being used as an outcome in high profile RCTs (as mentioned in Section 4.5.1, RSFDs or organ support-free days have been used as the primary endpoint in several recent high-profile RCTs [83-85]), these proposed statistical considerations can serve as a reference point for RSFD analyses in future clinical trials. Thus, we believe this to be one of the statistical innovations proposed by the Data Coordinating Center (DCC) for this Phase 3 trial.

One important limitation to using RSFDs as an endpoint arises, as previously stated, due to its composite nature. RSFD assigns points based on counting back from day 28 to the last day when respiratory support was received (see Section 6.1.1). The outcome also considers mortality and assigns an overall score of zero points to those who die within those first 28 days. Thus, the composite nature of this endpoint leads to it being a zero-inflated binomial random variable, which has a mixture distribution of a degenerate 0 and a binomial distribution. That is, we can write

$$RSFDs \sim \pi \times 0 + (1 - \pi) \times Bi(28, p)$$

where π is the probability that a death occurs, and $Bi(28, p)$ is a binomial distribution such that p is the probability of a subject experiencing a RSFD while being alive through the specified window, that is desired to be modeled. The zero inflated binomial response is a special instance of over-dispersed responses, and there is considerable literature on the numerous challenges and

statistical issues when modeling such data [92, 93]. Thus, modeling of RSFDs can be handled through a number of approaches:

1. Account for over-dispersion through the zero-inflated binomial model: The zero-inflated binomial model is obtained by mixing a degenerate distribution at zero with a standard binomial distribution [94, 95], and has been subsequently used in epidemiology and health economics to model binomial counts with excessive zeros. The zero-inflated binomial model will be used as an alternative approach to model RSFDs in this analysis.

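### The zero-inflated binomial model for RSFDs gives survivors plain binomial variance, which the Phase 2 data contradict; separately, the quoted binomial SD of 6.67 days is impossible as written

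*Combined protocol and SAP*

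**What the plan says.** Protocol section 6.2.2, under the paragraph on alternative approaches, introduces the work this way: "Our secondary analysis plan also includes a pipeline for exploring alternative approaches to analyze RSFDs". It describes RSFDs as a variable "which has a mixture distribution of a degenerate 0 and a binomial distribution", "where π is the probability that a death occurs", with Bi(28, p) for everyone else. Three approaches follow. The first is presented as a way to deal with over-dispersion: "The zero-inflated binomial model will be used as an alternative approach to model RSFDs in this analysis". The second is a beta-binomial model, and the third models mortality and time off support separately. For the first, the protocol gives no variance estimator, test, dispersion parameter or check of fit.

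The note to Table 6-2 in section 6.1.1 compares a binomial SD for Phase 2 VFDs with the observed one. It says the binomial SD "is estimated to be 6.67 days, smaller than the empirical estimate of 9.4 days, which suggests a substantial over-dispersion", and uses this to justify a normal model with the empirical variance.

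The separate SAP does not mention the zero-inflated binomial. Its section 12, on changes from the protocol, does not say that it was dropped.

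**The concern.** Zero inflation explains the excess of zeros. It does nothing for the spread of the non-zero values. A binomial count of 28 assumes 28 independent days with a common probability. Under the last-off rule in section 6.1.1, a single date fixes a survivor's whole count, so the days are close to perfectly dependent and survivors differ far more than a binomial allows. A model without a term for that spread gives standard errors for p that are too small if they come from its own likelihood.

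The zero component is also mislabelled. A survivor still on support at day 28 scores 0 (the third worked example in section 6.1.1), and the model can absorb that patient only into the probability it calls death.

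At stake is a committed alternative analysis that could report a significant effect on p where the t-test shows none. The figure of 6.67 adds to this: it tells the reader that the gap from a plain binomial is modest in size when it is large.

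**Working it through.** **1. The plan's own figures.** Table 6-1 gives the Phase 2 sepsis cohort (columns n, min, Q1, median, mean, Q3, max, SD): "Total 137 0 13.0 23 17.75 25 27 9.50". By arm, the control group has n 66, mean 16.33, SD 9.62, and the treatment group n 71, mean 19.07, SD 9.25.

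- Pooled SD = sqrt[(65 × 9.62² + 70 × 9.25²)/135] = 9.43, which agrees with the stated 9.4.
- Table 6-2 reproduces exactly with a t-test power solver at 2.74 days: 186, 213 and 249 per arm.
- The binomial SD does not reproduce. SD = sqrt[28p(1−p)] with p = mean/28:

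| Group | p | Variance | SD |
|---|---|---|---|
| Total | 0.634 | 6.50 | 2.55 |
| Control | 0.583 | 6.81 | 2.61 |
| Treatment | 0.681 | 6.08 | 2.47 |

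The largest possible value, at p = 0.5, is sqrt(7) = 2.65. The variance ratio implied by the text is (9.4/6.67)² = 2.0. The ratio against the correct binomial SD is 9.4²/6.50 = 13.6.

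**2. Survivors' spread, taken directly.** Table 2-1 (section 2.5.3) gives ventilation days in survivors as median 6.5 (IQR 3-12.25) on placebo and 4 (2.25-7) on ganciclovir. A survivor's VFDs are 28 minus this duration, so the variance is the same. I approximate SD as IQR/1.349 and use p = median/28 for the binomial.

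- Placebo: SD 9.25/1.349 = 6.86, variance 47.0. Binomial variance 28 × 0.232 × 0.768 = 4.99. Ratio 9.4.
- Ganciclovir: SD 4.75/1.349 = 3.52, variance 12.4. Binomial variance 28 × 0.143 × 0.857 = 3.43. Ratio 3.6.

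This step needs no assumption about the share of zeros.

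**3. What that does to a model-based test.** If the true variance is φ times the one assumed, a nominal two-sided 5% test rejects under the null with probability 2[1 − Φ(1.96/√φ)]. For φ = 9.4 this is 52%, and for φ = 3.6 it is 30%.

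**4. The same from the overall moments.** With zero fraction π, the non-zero mean is μ = 17.75/(1−π) and the non-zero variance is [SD² − π(1−π)μ²]/(1−π). The documents do not give π, so it is varied. For example, at π = 0.15 and SD 9.4: μ = 20.88, variance (88.36 − 55.60)/0.85 = 38.5 (SD 6.2), binomial variance 5.31 (SD 2.3), φ = 7.3.

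| Zeros | False rejection, SD 9.4 | False rejection, SD 9.5 |
|---|---|---|
| 12% | 52% | 53% |
| 15% | 47% | 48% |
| 20% | 22% | 27% |
| 21% | 9% | 15% |

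The mean, SD and quartiles in Table 6-1 cap the zero fraction at about 21-22%.

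**5. Simulation.** Null trials with 250 per arm (1,500 per scenario) were drawn from distributions matched, within small tolerances, to the mean, SD and quartiles in Table 6-1. The zero-inflated binomial likelihood-ratio test of p rejected in 53% (12% zeros), 45% (15%), 43% (17%), 34% (19%), 27% (20%) and 20% (21%). The last figure exceeds step 4 because the matched distribution had a slightly larger SD (9.55), and the result is very sensitive there. A joint test of p and π rejected in 16-47% over the same range. An empirical variance for the non-zero days gave 4.6-5.7%, and the t-test on all patients 4.5-5.5%. When the data truly followed a zero-inflated binomial, the two likelihood-ratio tests gave 4-5%, so misfit is the cause.

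**The case against.** Several points on the other side stand.

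- **No test is specified.** A reader might infer that the planned p-values will be false positives at the rates above. The documents do not support that: no standard error or test is named, and a robust variance removes the inflation.
- **The size is fragile.** The zero fraction is unstated, and near 20% one percentage point changes the answer from 22% to 9%. The 20% mortality in section 6.1.2 is a Phase 3 planning value, whereas Table 6-3 footnotes 15% as the Phase 2 figure. Deaths and zeros are also not the same thing.
- **The over-dispersion is not concealed.** A reader might infer that 6.67 hides the problem. Section 6.1.1 calls the over-dispersion substantial and draws the right conclusion from it, and section 4.5.1 expects a bimodal distribution. The figure understates the size; it does not hide the fact.
- **6.67 may be a mislabel.** It is near the binomial variance (6.50 overall) but equals none of the computed variances. A zero-inflated binomial with mean 17.75 and about 11% zeros has an SD of about 6.67. Replacing it with 2.55 without asking could be a mis-correction.
- **It is not singled out as a reference method.** The protocol's remark that this work could serve future trials covers the set of approaches, not this model alone.
- **Other analyses are planned.** The beta-binomial has a dispersion parameter, and the t-test, permutation test and semiparametric estimate carry the primary inference. These limit the consequences but do not repair this model's own standard errors, and no rule says how conflicting results would be read.

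**Conclusion.** The concern holds in limited form. As written, the zero-inflated binomial cannot account for the over-dispersion it is meant to address, because survivors' variance is about 9 (placebo) and 4 (ganciclovir) times binomial in the protocol's own data. With model-based inference, a nominal 5% test of p would reject falsely about 20-50% of the time for 12-20% zeros, and about 9-15% by the moment calculation at 21%. This rests on three assumptions: model-based standard errors or likelihood-ratio tests, a zero fraction in that range, and Phase 2 VFDs as a proxy for RSFDs (the protocol makes the same substitution for the variance). The direction is secure; the exact rate is not.

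The 6.67 is certain to be wrong as a plain binomial SD; what was meant is not certain. A reader might infer that the sample size or primary result is compromised. Neither is: both rest on the empirical SD or the t-test, and no decision rule uses this model.

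**What to change.** In section 6.2.2, or in the SAP if the analysis is kept, replace the first approach with a zero-inflated or hurdle beta-binomial. Alternatively, keep the zero-inflated binomial for point estimates and state that standard errors come from a sandwich estimator or bootstrap. Add a check of fit for the survivors' distribution, and describe π as the excess-zero probability, not the death probability.

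In the note to Table 6-2, have the sponsor trace 6.67. If a plain binomial was meant, restate it as an SD of about 2.55 days (variance about 6.5). If it is the SD of a zero-inflated binomial, relabel it and give the zero fraction used.

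The SAP should also say whether this analysis is still planned. The cost is a line or two of text and a different model call, with no new data and no change to the primary analysis or sample size.

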10. SECONDARY ENDPOINTS ANALYSES

Each secondary endpoint will be analyzed and summarized using appropriate statistical methods, and results will be presented by treatment group unless otherwise specified. Tables or figures will be used where appropriate.

1. Ventilator-Free Days (VFDs) defined as 28 days minus the total duration (in days) of invasive mechanical ventilation during the first 28 days post-randomization.
 - Participants who do not survive through Day 28 will be assigned 0 VFDs.
 - Participants who remain mechanically ventilated on Day 27 will be assigned 0 VFDs.
 - Participants transferred to long-term acute care hospitals (LTACHs) will be assigned 0 VFDs.
 - Participants who withdraw from the study will be considered as having missing data.Differences in VFDs between treatment arms will be analyzed using a two-sample parametric t-test. Descriptive statistics (mean, standard deviation, median, quartiles, and range) will also be presented in summary tables.
2. Total RSFDs without last-off approach defined as 28 minus the cumulative number of days on any form of respiratory support within 28 days of randomization, without the last-off rule applied. Participants who die before Day 28 will be assigned 0 RSFDs.

Differences in RSFDs between treatment arms will be analyzed using a two-sample parametric t-test. Descriptive statistics (mean, standard deviation, median, quartiles, and range) will also be presented in summary tables.

3. Mortality will be evaluated as a time-to-event outcome through 28 days and 180 (± 42 days). Analyses will mirror those described in Section 9, including Kaplan–Meier survival curves, log-rank tests, and Cox proportional hazards models (adjusted and stratified by baseline creatinine clearance). In addition, we will test for an interaction between treatment group and period (during- vs. post-treatment) to determine if treatment effects on mortality vary over time.
4. Duration of mechanical ventilation among participants who survive through Day 28, the total number of days on invasive mechanical ventilation will be calculated. Participants transferred to LTACHs will be assigned 28 days. Differences between treatment arms will be analyzed using a two-sample parametric t-test. Descriptive statistics (mean, standard deviation, median, quartiles, and range) will also be presented in summary tables.

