5.2.1 Secondary Endpoints

1. VFDs (defined to be 28 days minus the duration of mechanical ventilation through day 28 since randomization [a key secondary endpoint]). Participants who do not survive through day 28 are assigned zero VFDs.
2. Total RSFDs (calculated as 28 days minus each day of respiratory support through day 28 since randomization). Participants who do not survive through day 28 are assigned zero respiratory-support-free ventilator-free days.
3. Mortality by day 180 (day 28, day 180, time-to-event).
4. Duration of mechanical ventilation (among survivors) by day 28.
5. Duration of respiratory support (among survivors) by day 28.
6. Oxygenation (PaO₂/FiO₂ ratio) daily on study days 1-7.
7. ICU-free days by day 28.
8. CMV DNA detection in plasma and endotracheal aspirate (ETA) by day 28 (>0 IU/mL, >1000 IU/mL).
9. Number of patients with reportable adverse events of Grade 3 or higher by day 28.

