2. Account for over-dispersion through the beta-binomial model: The beta-binomial distribution is a discrete probability distribution which arises when the probability of success in a fixed number of Bernoulli trials is either unknown or random. It has frequently been used in classical statistics to capture over-dispersion in binomial type distributed data [96, 97], and this will be used as another alternative approach.
3. Separate modeling of composites: In addition to the above approaches, the composite outcome will also be modeled separately for the primary analysis population and considered for assessment. Mortality will be modeled as a time to event outcome, and the Cox model will be used to evaluate whether the treatment (ganciclovir) has any effect on time to death. On the other hand, duration of time off respiratory support (total time in days not spent receiving respiratory support within the first 28 days), regardless of the mortality status, will be analyzed separately in a Generalized Linear Model to evaluate if ganciclovir increases total time off respiratory support within the first 28 days.

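### On its literal reading, the supportive model of time off respiratory support counts days after death as days off support, which biases it toward the arm with more deaths

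*Combined protocol and SAP*

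**What the plan says.** Protocol Section 6.2.2 lists three alternative ways to analyse respiratory-support-free days (RSFDs). In the third, "the composite outcome will also be modeled separately for the primary analysis population and considered for assessment". For the mortality component, "the Cox model will be used to evaluate whether the treatment (ganciclovir) has any effect on time to death". The other component is time off support, defined as "total time in days not spent receiving respiratory support within the first 28 days". It is taken "regardless of the mortality status, will be analyzed separately in a Generalized Linear Model", and the model is fitted "to evaluate if ganciclovir increases total time off respiratory support within the first 28 days".

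Elsewhere the plan sets a score for deaths. For the primary endpoint, protocol Section 6.1.1 says: "Participants who do not survive to day 28 are assigned zero respiratory-support-free days". Total RSFDs, the second secondary endpoint in Section 5.2.1, are "calculated as 28 days minus each day of respiratory support through day 28 since randomization", again with zero for deaths by day 28. SAP Section 10 repeats that rule: "Participants who die before Day 28 will be assigned 0 RSFDs".

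The SAP does not list the component model. Section 12 of the SAP, on changes from the protocol, does not withdraw it either.

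**The concern.** Total RSFDs and the component outcome are the same count: 28 minus the days on support. In the first, an explicit zero stops days after death from being credited. The component model drops that zero, keeps the fixed 28-day window and includes deaths, but says nothing about days after death. A dead patient receives no support, so the definition as worded credits those days. Because an increase is read as benefit, more deaths push the result in the favourable direction for that arm, whichever arm it is.

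The component analysis has a specific job. Section 4.5.1 concedes that RSFDs cannot show effects that run in opposite directions, such as higher mortality with shorter support in survivors. Modelling the components separately is where a reader would look for that pattern. If the non-mortality component absorbs deaths with the wrong sign, it can suggest such a pattern when survivors do not differ at all.

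**Working it through.** **1. The plan's own scoring.** The three examples in protocol Section 6.1.1 reproduce as 28 minus the last day of support: 28 - 10 = 18, 28 - 26 = 2, 28 - 28 = 0. The documents give no figure for the component model, so the rest is illustration.

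**2. Scoring a death.** Take a patient on support until death on day D.
- Component outcome, read literally: 28 - D. For D = 3 this is 25 days, against 18 for the survivor in the first example.
- Zero rule, or days alive and off support: 0.

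If the patient came off support before dying, after s days of support, the literal score is 28 - s and days alive and off support are D - s. The excess is again 28 - D.

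**3. When a death outscores the average survivor.** This happens when 28 - D exceeds S, the survivors' mean days off support. The documents do not give S for RSFDs. As a proxy, take the Phase 2 control mean of 16.33 ventilator-free days (Table 6-1; deaths score zero) and divide by 1 - m, where m is control mortality. Table 6-3 marks 15% as the Phase 2 figure; 10% to 25% shows the range.

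| m | S = 16.33/(1 - m) | Break-even day, 28 - S |
|---|---|---|
| 10% | 18.1 | 9.9 |
| 15% | 19.2 | 8.8 |
| 20% | 20.4 | 7.6 |
| 25% | 21.8 | 6.2 |

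**4. Difference between arms.** Assume identical survivors in both arms, support until death, and one common day of death. Let d be ganciclovir mortality minus placebo mortality.
- Deaths scored zero, or days alive and off support: -d × S
- Literal: d × (28 - D) - d × S
- Bias, literal minus the first: d × (28 - D)

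The 20% placebo mortality is the planning figure in Section 6.1.2. The 25% and 30% on ganciclovir and the days of death are assumptions. With S = 19.2:

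| Day of death | Literal, 20% v 25% | Literal, 20% v 30% |
|---|---|---|
| 3 | +0.29 | +0.58 |
| 5 | +0.19 | +0.38 |
| 7 | +0.09 | +0.18 |
| 10 | -0.06 | -0.12 |
| 14 | -0.26 | -0.52 |
| Any day, days alive and off support | -0.96 | -1.92 |

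For example, at 20% v 30% and day 10, the bias is 0.10 × 18 = 1.80 days, and -1.92 + 1.80 = -0.12.

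**5. Against the noise.** With the planning SD of 9.4 days as a proxy and the planned 250 per arm, the standard error is 9.4 × √(2/250) = 0.84 days. A literal +0.38 is under half a standard error. The shift that produces it, 0.10 × 23 = 2.30 days, is more than two and a half.

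**The case against.** The strongest reply is that this is an omission and not a rule. The protocol never says that days after death count. Disregarding mortality status could mean only that deaths stay in the model without the zero, credited with the days they actually lived off support. That reading is possible and would remove the bias, but the text does not state it. The words as they stand define a count over a fixed window, and the two readings can give opposite signs.

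The second reply is that little depends on this model, and that stands. It is one of several exploratory alternatives and sits beside a Cox model for death. SAP Sections 9 and 10 add Kaplan-Meier, log-rank and Cox analyses to days 28 and 180. The primary and total-RSFD analyses score deaths as zero. Section 6.2.2 also already plans the survivor comparisons of ventilation and support duration, with a sensitivity analysis for truncation by death if death rates differ.

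Third, a sign change needs early deaths, and Section 7.4 excludes patients expected to survive less than 72 hours. That also stands: the usual effect is attenuation. An apparent gain of a few tenths of a day would not by itself be read as benefit.

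A reader might go further and infer that the plan hides a mortality harm, pointing to SAP Section 4, where enrollment closed on safety and futility concerns. The documents do not support this. Neither reports mortality by arm, and one supportive model cannot conceal an excess that several planned mortality analyses would show.

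**Conclusion.** The point holds for this supportive model only. Taken literally, its outcome counts days after death as days off support and biases the comparison toward the arm with more deaths, by the mortality difference times (28 minus the day of death) for patients on support until death. Harm is attenuated in general. The sign changes only when deaths fall before about day 6 to 10, for survivor means of about 18 to 22 days. A mortality benefit would be understated in the same way.

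The formula follows from the definition. The sizes rest on assumptions that the documents do not supply: ganciclovir mortality, the day of death, support until death, identical survivors, and Phase 2 ventilator-free days standing in for RSFDs. The tempting stronger conclusion, that early deaths would pass as a convincing treatment benefit or that the trial's main results are at risk, is not supported.

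**What to change.** In the third alternative analysis of protocol Section 6.2.2, define the outcome as days alive and off respiratory support through day 28, and state that days from death onward do not count. Carry the same sentence into the SAP if the model is to be run; otherwise record in SAP Section 12 that it is dropped.

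Days alive and off support still falls as deaths rise, so it does not isolate support duration. It should be interpreted beside the Cox model and beside the survivor-duration comparisons with the truncation-by-death sensitivity analysis already planned in Section 6.2.2.

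The cost is one sentence. Respiratory support and vital status are already collected, so no new data are needed, and no other analysis changes.
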